Research plan, translated from Swedish, including a statistical analysis plan

A controlled study of weighted chain blankets

Document Date: November 1, 2015

Scientific description

Purpose

The primary aim is to investigate whether the nightly use of a weighted chain blanket has a significantly better effect on sleep time, total sleep time and daytime fatigue for patients with sleep disturbance in psychiatric disease compared to a light chain blanket (equivalent to placebo) after four weeks of use. Secondary issues are whether treatment with weighted chain blanket results in a significantly better effect than a light blanket for objectively measured sleep and subjectively assessed anxiety, depression, and pain.

Hypotheses

The use of the weighted chain blanket allows:

1. Sleep time decreases.
2. Sleep stays longer with fewer wake-ups during the night.
3. The sleep becomes calmer
4. The sleep becomes less tense
5. Pain decreases daytime
6. Pain decreases at night
7. Anxiety and anxiety decrease daytime
8. Anxiety and anxiety decrease at night
9. Fatigue decreases daytime
10. Concentration capacity increases daytime

Primary outcome measures

The patient's subjective symptoms of sleep and day fatigue will be evaluated by the Insomnia Sleep Inventory (ISI) and the Fatigue Scale Inventory (FSI) scales. It will also be evaluated by the patient's self-assessed values in the self-assessment rating scale developed by Stockholm Utility for evaluating ball and chain blankets (hereafter referred to as "rating scale for weighted blankets"). Depression and anxiety will be evaluated with the scale Hospital Anxiety and Depression Scale (HAD). Objective sleep parameters will be recorded with actigraphs.

Chief researcher

Responsible for the study of patients with bipolar disorder and/or ADHD is [name], leg. Occupational Therapist at the Affective Section, Psychiatry Southwest of Stockholm County Council (SLSO) and [name], Medical Doctor and Chief Physician and Section Manager at the Affective Section, Psychiatry Southwest in Stockholm County Council (SLSO)

Overview

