After the patient has received oral information and signed a written informed consent, characterization of the patient material will be made. The study will be conducted in four phases. The first week they use their usual blanket (baseline). Sleep, fatigue, anxiety, and depression will be recorded with the scales mentioned above. Then a second part follows four weeks when they use the blanket randomized to (Week 2-5). In the second phase, patients are randomized to either get a 6 or 8 kg lining blanket or a lightweight cover of approximately 1.5 kg of the same appearance in which light plastic chains are sewn in. This cover is of such low weight that it corresponds to a regular blanket and therefore acts as a placebo control. Randomization and instruction, as well as collection of blankets after four weeks of use, will be carried out by a person who does not perform the ratings at inclusion and follow-up. Patients should maintain their medication unchanged during the study period. They are followed up by telephone every week. At the telephone interview information about how they used the blanket will be gathered, and patients will estimate their sleep with the scales mentioned above. After four weeks of use of the blanket, the final visit for the randomized study will be conducted, and data (scales and actigraph) from this visit is the primary outcome of the study.

In the third phase, all patients are offered an open-follow up study in a 4-week (week 6-9) where they can choose freely between ball and chain weighted blankets. After these four weeks, everyone is called for a second visit with new estimates and collection of actigraph data of (week 9). In the fourth phase, patients who wish to continue with one of the weighted blankets will be offered to do so. After 12 months, patients who choose to continue using weighted blankets will be contacted by telephone to check the extent to which they use the blanket and are asked to estimate the same symptoms as before.

Power Calculation

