In a previously uncontrolled pilot study of weighted-duty non-control groups, the average sleep time decreased from 98 minutes (SD 69) to 31 minutes (SD 28). Based on these results, calculating the effect of the blanket for a future study where the placebo deck had no effect, and the active blanket would have the same effect as in the pilot study figures would want a power of 0.9 with a significance level of 0.05, only 15 subjects would be required in the study. However, we have no data on the effect of sleep on sleep measured with the ISI scale. Nor is it likely that the placebo blanket would not have any effect at all. However, we expect that patient material of about 100 individuals should be enough to find a significant effect.

Statistical analysis

Comparison between the effect on the groups will be performed after four weeks and eight weeks with conventional methods of statistical significance testing in controlled and randomized studies. All patients who used the blanket for at least one night will be included in the analysis (equivalent to "intention to treat"). Data from patients who discontinue treatment will be asked if they can accept to participate in follow-up in the same way as if they had completed treatment. In these cases, data are included in the analysis as measured. Secondly, Last Observation Carried Forward (LOCF) or other established statistical method is used to handle data from patients who interrupt treatment.

Self-assessed values before, after eight weeks and 12 months will be analyzed with and at eight weeks after with paired t-test for dependent variables. When data distribution does not match normal distribution, the analysis will be supplemented by non-parametric tests.

Timetable

The study will extend over three years.

Safety monitoring

Clinical monitoring will be done by treatment staff on the Affective section in consultation with the patient.

Ethical considerations

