Testing/ordination of the chain blanket in sleep disorders, as well as motor anxiety and/or mental anxiety, is a well-known occupational therapy intervention. The method appears effective and has no significant adverse effects. However, the method is not sufficiently illuminated and scientifically tested. The use of the clinical data recorded as part of routine follow-up will be unidentified and therefore does not present a disadvantage to the patient. All procedures will be done with informed consent, data will be processed with confidentiality and unidentified. We believe that the disadvantages of the patients are small.

Possible impact

Sleep disturbances caused by anxiety are one of the common causes of suffering for patients with psychiatric diagnoses. If it is confirmed in this study that the chain blankets can reduce this disorder for the patient group without having any side effects of treatment, it will represent a very big step forward for the treatment of sleep disturbances.

References

2. Cappuccio F,ea. Sleep Duration and All-Cause Mortality: A Systematic Review and Meta-Analyses of Prospective Studie.pdf>. Sleep. 2010;33(5).

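### The protocol names freedom from side effects as something this study could confirm, but describes no systematic collection or between-arm comparison of adverse effects

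*Protocol*

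**What the plan says.** Three sections of the protocol bear on harm.

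- Possible impact sets out the hoped-for result: "If it is confirmed in this study that the chain blankets can reduce this disorder for the patient group without having any side effects".
- Ethical considerations gives the starting belief: "The method appears effective and has no significant adverse effects". It also says "We believe that the disadvantages of the patients are small".
- Safety monitoring is a single sentence: "Clinical monitoring will be done by treatment staff on the Affective section in consultation with the patient".

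The sections on data and analysis are as follows.

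- Procedure, weekly contact: "At the telephone interview information about how they used the blanket will be gathered, and patients will estimate their sleep with the scales mentioned above".
- Procedure, visit after four weeks of blanket use: "data (scales and actigraph) from this visit is the primary outcome of the study".
- Primary outcome measures lists ISI, FSI, the rating scale for weighted blankets, HAD and actigraphy. Purpose adds pain as a secondary comparison.
- Statistical analysis: "Comparison between the effect on the groups will be performed after four weeks and eight weeks". No comparison of harms is named. Patients who discontinue are asked to remain in follow-up, but recording why they stopped is not mentioned.

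**The concern.** A statement that a treatment works and has no side effects makes two claims, and each needs data. The protocol provides for the first in detail. For the second it defines no adverse effect, sets no question or form, and plans no tabulation by arm. If the plan were followed exactly, there would be no systematic count of unwanted effects in either arm.

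Two things are at stake. One is the balance of benefit and harm that readers would take from the trial. The other is the comparison itself. Only the four randomised weeks (study weeks 2 to 5) set a weighted blanket against a light one. From week 6 all patients are offered a free choice of weighted blankets, so harm information not gathered in the randomised weeks cannot be recovered later in controlled form.

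**Working it through.** The protocol states no harm rate, no margin and no sample size for safety, so there is no figure to reproduce. The check has two parts.

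**1. Does any planned element supply harm data by arm?**

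- Purpose, Hypotheses and Primary outcome measures: sleep, fatigue, anxiety, depression, pain, concentration and actigraphy. These can show worsening by arm on those symptoms. There is no tolerability outcome. The items of the blanket rating scale are not shown, so its content cannot be judged.
- Weekly calls: blanket use and sleep ratings. No question on unwanted effects is described.
- Visit after four weeks of use: scales and actigraph.
- Safety monitoring: clinical monitoring by staff, with no definition, form, schedule or analysis by arm.
- Statistical analysis: effect comparisons only.

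Result: partial coverage through the efficacy measures, and no systematic coverage of other unwanted effects or of stopping because of them.

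**2. With full collection, could the trial confirm that there are no side effects?**

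Inputs: about 100 patients in total (Power Calculation). The allocation ratio is not stated. I assume 1:1, which gives n = 50 on a weighted blanket.

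The exact upper limit for the true rate when 0 of n patients have an event is 1 − α^(1/n), with α = 0.05 for a one-sided 95% limit and α = 0.025 for a two-sided 95% interval.

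- n = 50: 1 − 0.05^(1/50) = 5.8%; 1 − 0.025^(1/50) = 7.1%.
- n = 60 (if more patients were allocated to the weighted blanket): 4.9% and 6.0%.
- n = 100 (if every patient took a weighted blanket in the open phase, hence uncontrolled): 3.0% and 3.6%.

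The chance of seeing no event in 50 patients at a true rate p is (1 − p)^50. The rates are assumed for illustration.

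- p = 1%: 0.99^50 = 61%.
- p = 2%: 0.98^50 = 36%.
- p = 5%: 0.95^50 = 8%.

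To illustrate incomplete capture, suppose that only half of the events at a true 5% rate were recorded (an assumption; the protocol gives no basis for a capture rate). The recorded rate is then 0.05 × 0.5 = 0.025, and the chance of no recorded event is 0.975^50 = 28%, against 8% with full capture.

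A formal comparison between arms of 50 would also be weak. Power at two-sided 0.05 is about 38% for 5% against 15%, 39% for 2% against 10%, and 62% for 5% against 20% (all rates assumed). This supports descriptive reporting with intervals rather than a test.

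**The case against.** The strongest reply is that no safety conclusion is planned. The sentence is conditional and stands under Possible impact, outside the aims, hypotheses and analysis. The document is a translation with visible faults, so one absolute word should not bear much weight. ISI, FSI, HAD and pain are measured in both arms and would show some harms. Monitoring is planned in consultation with the patient. The zero-event limit applies to any trial of this size and does not by itself show an error.

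Much of this stands, and it rules out several stronger readings that a reader might infer.

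- That the plan expects to show freedom from side effects. The text only names it as a possible finding.
- That the plan presumes there are no harms at all. It speaks of no significant ones and of small disadvantages.
- That no harm information is collected by arm. Symptom worsening is measurable, and the rating scale items are unknown.
- That missing records would be treated as proof of no harm. No such rule is written.
- That a faulty harm conclusion would feed into the open phase. That phase is offered to each patient straight after the randomised weeks and depends on no trial result.

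What the reply does not meet is the mismatch itself. The statement refers to confirmation in this study, and nothing described would supply the evidence. A separate analysis plan could not repair this, because what is asked at calls and visits is protocol content, and harms that were not recorded cannot be analysed afterwards.

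**Conclusion.** The concern holds in this limited form: the protocol names a harm finding that its described data collection could not support. The efficacy measures would show only worsening of the symptoms they cover, and the only controlled window for observing other harms is four weeks long.

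The 5.8% and 7.1% limits rest on the assumed 1:1 split of about 100 patients. The 28% and 8% figures also rest on an assumed 5% harm rate and, for the first, on assumed half capture. They illustrate size and are not estimates for this trial. The conclusion that zero events could not confirm the absence of side effects holds at every arm size shown.

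The primary efficacy result is unaffected. This is an inexpensive improvement that should be made, and it does not invalidate the trial.

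**What to change.** - Ask one fixed question on unwanted effects, and record the reason for any stopping of use, in the same words in both arms. Ask it at each weekly call, at the visit after four weeks of blanket use (end of study week 5) and at the week-9 visit.
- Tabulate the counts by randomised arm for the four randomised weeks, with exact 95% confidence intervals. Report the open phase separately, labelled as uncontrolled.
- In Possible impact, replace the closing claim about side effects with a statement of the observed rate of unwanted effects and its upper confidence limit.

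The cost is one extra question at contacts already planned, one descriptive table and a more modest claim. The primary outcome, sample size and efficacy analysis do not change.
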